12.2.6. Footnotes

- A solid line spanning the margins will separate the body of the data display from the footnotes.
- All footnotes will be left justified with single-line spacing immediately below the solid line underneath the data display.
- Footnotes should always begin with "Note:" if an informational footnote, or 1, 2, 3, etc. if a reference footnote. Each new footnote should start on a new line, where possible.
- Footnotes will be used sparingly and add value to the table, figure, or listing. If more than six lines of footnotes are planned, then a cover page is strongly recommended to be used to display footnotes, and only those essential to comprehension of the data will be repeated on each page.
- The last line of the footnote section will be a standard source line that indicates the name of the program used to produce the data display, and date the program was run (i.e., 'Program : myprogram.sas Table Generation: ddmmmyyyy').

This document is confidential.

13. Quality Control

SAS programs are developed to produce output such as analysis data sets, summary tables, data listings, and figures. An overview of the development of programs is detailed in Syneos Health SOP Developing Statistical Programs (3907)

Syneos Health SOPs Developing Statistical Programs (3907) and Conducting the Transfer of Biostatistical Deliverables (3908) describes the quality control procedures that are performed for all SAS programs and output. Quality control is defined here as the operational techniques and activities undertaken to verify that the SAS programs produce the output by checking for their logic, efficiency and commenting and by review of the produced output.

This document is confidential.

14. Index of Tables

The following tables will be produced (table numbers and titles may be different in the final versions):

Header	Table Number	Name	Analysis Set
14.1		Demographic Data Summary Tables	
	14.1.1	Subject Disposition Summary	Enrolled Set
	14.1.2.1	Protocol Deviations Summary	Safety Set
	14.1.2.2	Protocol Deviations Due to COVID-19 Summary	Safety Set
	14.1.3.1	Demographics and Baseline Characteristics Summary	miITT Set
	14.1.3.1a	Demographics and Baseline Characteristics Summary by Treatment Group (CL)	miITT Set
	14.1.3.1b	Demographics and Baseline Characteristics Summary	ITT Set
	14.1.3.2	Medical History Summary	Safety Set
	14.1.3.2a	Medical History Summary by Treatment Group (CL)	Safety Set
	14.1.4.1	Prior Medications Summary	Safety Set
	14.1.4.2	Concomitant Medications Summary	Safety Set
	14.1.5	Extent of Exposure Summary	Safety Set
	14.1.5a	Extent of Exposure Summary	Safety Set
	14.1.6	Treatment Compliance Summary	Safety Set
14.2		Efficacy Data Summary Tables	
	14.2.1.1.1	YGTSS-TTS: Summary	miITT Set
	14.2.1.1.1a	YGTSS-TTS: Summary by Treatment Group (CL)	miITT Set
	14.2.1.1.1b	YGTSS-TTS: Summary	ITT Set
	14.2.1.1.2	YGTSS-TTS: Subscales Summary	miITT Set
	14.2.1.1.2b	YGTSS-TTS: Subscales Summary	ITT Set
	14.2.1.1.3	YGTSS-GS: Summary	miITT Set
	14.2.1.1.3b	YGTSS-GS: Summary	ITT Set
	14.2.1.1.4	YGTSS-Impairment: Summary	miITT Set
	14.2.1.1.4b	YGTSS-Impairment: Summary	ITT Set
	14.2.1.1.5	YGTSS-TTS: Subjects with a >= 25% Improvement	miITT Set
	14.2.1.2	CGI-TS-S: Summary	miITT Set
	14.2.1.2b	CGI-TS-S: Summary	ITT Set
	14.2.1.3	CGI-TS-I: Summary	miITT Set
	14.2.1.3b	CGI-TS-I: Summary	ITT Set
	14.2.1.4	C&A-GTS-QOL: Summary	miITT Set
	14.2.1.4b	C&A-GTS-QOL: Summary	ITT Set
14.3		Safety Data Summary Tables	
14.3.1		Adverse Events	
	14.3.1.1	Overall Summary of Adverse Events	Safety Set

This document is confidential.

Header	Table Number	Name	Analysis Set
	14.3.1.2.1	Summary of Adverse Events by Maximum Severity	Safety Set
	14.3.1.2.2	Summary of Adverse Events by Maximum Relatedness	Safety Set
	14.3.1.3.1	Summary of Adverse Events by System Organ Class and Preferred Term	Safety Set
	14.3.1.3.2	Summary of Adverse Events by System Organ Class, Preferred Term and Highest CTCAE Grade	Safety Set
	14.3.1.4.1	Summary of Treatment-Related Adverse Events by System Organ Class and Preferred Term	Safety Set
	14.3.1.4.2	Summary of Treatment-Related Adverse Events by System Organ Class, Preferred Term and Highest CTCAE Grade	Safety Set
	14.3.1.5.1	Summary of Adverse Events Leading to Treatment Termination by System Organ Class and Preferred Term	Safety Set
	14.3.1.5.2	Summary of Adverse Events Leading to Treatment Termination by System Organ Class, Preferred Term and Highest CTCAE Grade	Safety Set
	14.3.1.6	Summary of CTCAE Grade 3 or Higher Adverse Events by System Organ Class and Preferred Term	Safety Set
	14.3.1.7.1	Summary of Serious Adverse Events by System Organ Class and Preferred Term	Safety Set
	14.3.1.7.2	Summary of Serious Adverse Events by System Organ Class and Preferred Term by Age Group	Safety Set
	14.3.1.8.1	Summary of Adverse Events of Special Interest (AESI) for Parkinsonism by System Organ Class and Preferred Term	Safety Set
	14.3.1.8.2	Summary of Adverse Events of Special Interest (AESI) for Ecopipam by System Organ Class and Preferred Term	Safety Set
	14.3.1.9.1	Summary of Most common (>=5%) Adverse Event First Onset by Month	Safety Set
	14.3.1.9.2	Summary of Most common (>=5%) Adverse Events by Month (new incidence or ongoing)	Safety Set
14.3.4.1		Clinical Laboratory Data	

This document is confidential.

Header	Table Number	Name	Analysis Set
	14.3.4.1.1.1	Clinical Laboratory Results Summary: Hematology	Safety Set
	14.3.4.1.1.2	Shift from Baseline Summary: Hematology	Safety Set
	14.3.4.1.2.1	Clinical Laboratory Results Summary: Serum Chemistry	Safety Set
	14.3.4.1.2.2	Shift from Baseline Summary: Chemistry	Safety Set
	14.3.4.1.3.1	Clinical Laboratory Results Summary: Urinalysis	Safety Set
	14.3.4.1.3.2	Shift from Baseline Summary: Urinalysis	Safety Set
	14.3.4.1.4.1	Clinical Laboratory Results Summary: HbA1c	Safety Set
	14.3.4.1.4.2	Shift from Baseline Summary: HbA1c	Safety Set
14.3.4.2		Vital Signs	
	14.3.4.2.1	Vital Signs Summary	Safety Set
14.3.4.3		Electrocardiogram (ECG) Data	
	14.3.4.3.1	12-Lead Electrocardiogram Summary	Safety Set
	14.3.4.3.2	12-Lead Electrocardiogram Overall Interpretation Summary	Safety Set
14.3.4.4		Abnormal Physical Examination Results by Visit	
	14.3.4.4.1	Physical Examination Summary	Safety Set
14.3.4.5		Other Safety Data	
	14.3.4.5.1	Summary of Columbia Suicide Severity Rating Scale (C-SSRS)	Safety Set
	14.3.4.5.2	Summary of Abnormal Involuntary Movement Scale (AIMS) Total Score	Safety Set
	14.3.4.5.3	Summary of Barnes Akathisia Rating Scale (BARS)	Safety Set
	14.3.4.5.4	Summary of Children's Depression Rating Scale – Revised (CDRS-R) Raw Summary Score	Safety Set
	14.3.4.5.5	Summary of Pediatric Anxiety Rating Scale (PARS) Total Score	Safety Set
		Post-Hoc Analysis	
	14.3.4.6a	Shift from Baseline Summary: BMI z-score	Safety Set
	14.3.4.6b	Shift from Baseline Summary: Height z-score	Safety Set
	14.3.4.6c	Shift from Baseline Summary: Weight z-score	Safety Set
	14.3.4.7a	Shift from Baseline Summary: 12-Lead Electrocardiogram QTC	Safety Set
	14.3.4.7b	12-Lead Electrocardiogram Outliers	Safety Set

This document is confidential.

Statistical Analysis Plan for Interventional Studies

Sponsor: Emalex Biosciences, Inc.; Protocol No.: EBS-101-OL-001

Header	Table Number	Name	Analysis Set
	14.3.4.7c	Vital Sign: Heart Rate Outliers	Safety Set
	14.3.4.8	Shift from Baseline Summary: HbA1c	Safety Set
	14.3.4.9	Shift from Baseline Summary: Cholesterol	Safety Set

This document is confidential.

15. Index of Listings

Data collected in the database will be listed. Numbering of listings may be adjusted to accommodate split listings or listings that are omitted due to no records.

Header	Listing Number	Name	Analysis Set (Example)
16.2		Subject Data Listings	
	16.2.1.1	Subject Disposition	Enrolled Set
	16.2.1.2	Baseline Failure	Enrolled Set
16.2.2		Protocol Deviations	
	16.2.2.1	Protocol Deviations	Safety Set
	16.2.2.2	COVID-19 Study Disruptions	Enrolled Set
16.2.3		Subjects Excluded from the Efficacy Analysis	
	16.2.3.1	Analysis Population	Enrolled Set
	16.2.3.2	Inclusion/Exclusion Criteria	Enrolled Set
16.2.4		Demographic Data	
	16.2.4.1	Demographics and Baseline Characteristics	miITT Set
	16.2.4.1b	Demographics and Baseline Characteristics	ITT Set
	16.2.4.2	Medical History	Safety Set
	16.2.4.3	Psychiatric History	Safety Set
	16.2.4.4	Prior and Concomitant Medications	Safety Set
	16.2.5.1	Study Drug Administration	Safety Set
16.2.6		Individual Efficacy Response Data	
	16.2.6.1	Yale Global Tic Severity Scale (YGTSS)	miITT Set
	16.2.6.1b	Yale Global Tic Severity Scale (YGTSS)	ITT Set
	16.2.6.2	Clinical Global Impression of Tourette Syndrome (CGI-TS)	miITT Set
	16.2.6.2b	Clinical Global Impression of Tourette Syndrome (CGI-TS)	ITT Set
	16.2.6.3	Gilles de la Tourette Syndrome –Quality of Life Scale for Children and Adolescents (C&A-GTS-QOL)	miITT Set
	16.2.6.3b	Gilles de la Tourette Syndrome –Quality of Life Scale for Children and Adolescents (C&A-GTS-QOL)	ITT Set
16.2.7		Adverse Event Listings	
*	16.2.7.1	Adverse Events	Safety Set
	16.2.7.2	Serious Adverse Events	Safety Set
	16.2.7.3	Adverse Events Leading to Study Termination	Safety Set
	16.2.7.4	Adverse Events Leading to Death	Safety Set
	16.2.7.5	Adverse Events of Special Interest for Parkinsonism	Safety Set

This document is confidential.

Header	Listing Number	Name	Analysis Set (Example)
	16.2.7.6	Adverse Events of Special Interest for Ecopipam	Safety Set
16.2.8		Listing of individual laboratory measurements by patient	
	16.2.8.1	Clinical Laboratory Data	
	16.2.8.1.1	Hematology Laboratory Evaluations	Safety Set
	16.2.8.1.2	Biochemistry Laboratory Evaluations	Safety Set
	16.2.8.1.3	Urinalysis Laboratory Evaluations	Safety Set
	16.2.8.1.4	HbA1c Laboratory Evaluations	Safety Set
		Other Safety Data	
	16.2.8.2	Vital Signs	Safety Set
	16.2.8.3	12-Lead Electrocardiogram	Safety Set
	16.2.8.4	Physical Examination	Safety Set
	16.2.8.5.1	Columbia-Suicide Severity Rating Scale (C-SSRS) – Suicidal Ideation	Safety Set
	16.2.8.5.2	Columbia-Suicide Severity Rating Scale (C-SSRS) – Intensity of Ideation	Safety Set
	16.2.8.5.3	Columbia-Suicide Severity Rating Scale (C-SSRS) – Suicidal Behavior	Safety Set
	16.2.8.5.4	Columbia-Suicide Severity Rating Scale (C-SSRS) – Actual Attempts	Safety Set
	16.2.8.6	Abnormal Involuntary Movement Scale (AIMS)	Safety Set
	16.2.8.7	Barnes Akathisia Rating Scale (BARS)	Safety Set
	16.2.8.8	Children's Depression Rating Scale Revised (CDRS-R)	Safety Set
	16.2.8.9	Pediatric Anxiety Rating Scale (PARS)	Safety Set
	16.2.9.1	Height, Weight and BMI Z-Scores	Safety Set

This document is confidential.

16. Index of Figures

Header	Figure Number	Name	Analysis Set (Example)
14.2	14.2.1.4.1a	Mean (+/- SD) C&A-GTS-QOL Change from Baseline Total Score Over Time	miITT Set
	14.2.1.4.1b	Mean (+/- SD) VAS Change from Baseline Score Over Time	miITT Set
14.3	14.3.4.6a	Mean (+/- SD) BMI z-Score Over Time	Safety Set
	14.3.4.6b	Mean (+/- SD) Height z-Score Over Time	Safety Set
	14.3.4.6c	Mean (+/- SD) Weight z-Score Over Time	Safety Set

This document is confidential.

17. Appendices

17.1. Schedule of Assessments

Assessment ⁴	Baseline* (Titration)	Treatment												End of Study / Early Terminat ion	Follow Up Visit	Follow Up Phone Call
		0	1	2	3	4	5	6	7	8	9	10	11			
Study Month	0	1	2	3	4	5	6	7	8	9	10	11	12	One and TwoWee ks Post Last Dose	30 Days After Last Dose	
Study Visit Number	1	2	3	4	5	6	7	8	9	10	11	12	13	14 & 15		
Visit Window		±3days	±3days	±3days	±3days	±3days	±3days	±3days	±3days	±3days	±3days	±3days	±3days	±3days	±3days	±3days
Informed Consent	X															
Inclusion/ Exclusion	X															
Medical/Psychiatric/ medication History	X															
Physical Examination	X	X		X			X			X				X	X	
Vital Signs ¹	X	X	X	X	X	X	X	X	X	X	X	X	X	X	X	
ECG	X	X		X			X			X				X		
Laboratory Tests (Hematology and Chemistry) ²	X	X		X			X			X				X	X	
Urine Drug Screen	X	X		X			X			X				X		
Urine Pregnancy Test	X	X		X			X			X				X		

This document is confidential.

Assessment ⁴	Baseline* (Titration)	Treatment												End of Study / Early Terminat ion	Follow Up Visit	Follow Up Phone Call
		1	2	3	4	5	6	7	8	9	10	11	12			
Study Month	0													One and TwoWee ks Post Last Dose	30 Days After Last Dose	
Study Visit Number	1	2	3	4	5	6	7	8	9	10	11	12	13	14 & 15		
HbA1c		X		X			X			X				X		
YGTSS Score	X	X		X			X			X				X		
CGI-TS-I		X		X			X			X				X		
CGI-TS-S	X	X		X			X			X				X		
C&A-GTS-QOL	X	X		X			X			X				X		
Columbia Suicide Severity Rating Scale	X	X	X	X	X	X	X	X	X	X	X	X	X	X	X	X
Abnormal Involuntary Movement Scale (AIMS)	X	X	X	X	X	X	X	X	X	X	X	X	X	X		
Barnes Akathisia Ratings Scale (BARS)	X	X	X	X	X	X	X	X	X	X	X	X	X	X		
Children's Depression Rating Scale-Revised (CDRS-R)	X	X	X	X	X	X	X	X	X	X	X	X	X	X		
Pediatric Anxiety Ratings Scale (PARS)	X	X	X	X	X	X	X	X	X	X	X	X	X	X		
Adverse Events	X	X	X	X	X	X	X	X	X	X	X	X	X	X	X	X

This document is confidential.

Assessment ⁴	Baseline* (Titration)	Treatment												End of Study / Early Terminat ion	Follow Up Visit	Follow Up Phone Call
		1	2	3	4	5	6	7	8	9	10	11	12			
Study Month	0													One and TwoWee ks Post Last Dose	30 Days After Last Dose	
Study Visit Number	1	2	3	4	5	6	7	8	9	10	11	12	13	14 & 15		
Concomitant Medications	X	X	X	X	X	X	X	X	X	X	X	X	X	X	X	
Dispense Study Drug	X	X	X	X	X	X	X	X	X	X	X	X	X3			
Collect Unused Study Drug/Assess Drug Compliance		X	X	X	X	X	X	X	X	X	X	X	X	X	X	

Abbreviations: BP = blood pressure, CGI = Clinician Global Impression, CGI-TS-I = CGI Tourette Syndrome of Improvement, CGI-TS-S = CGI Tourette Syndrome of Severity, ECG = electrocardiogram, HbA1c = Hemoglobin A1c

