12.2. Adverse and Serious Adverse Events

12.2.1. Definition of Adverse Events

An AE is defined as any untoward medical occurrence in a subject administered a study drug and which does not necessarily have a causal relationship with this treatment. An AE can therefore be any unfavorable and unintended sign (including an abnormal laboratory finding), symptom, or disease temporally associated with the use of a study drug, whether or not related to the study

drug. In clinical studies, an AE can include an undesirable medical condition occurring at any time, including baseline or washout periods, even if no study treatment has been administered.

An abnormality identified during a medical test (e.g., laboratory parameter, vital sign, ECG data, physical examination) should be defined as an AE only if the abnormality meets one of the following criteria:

- Induces clinical signs or symptoms
- Requires active intervention
- Requires interruption or discontinuation of study medication
- The abnormality or investigational value is clinically significant in the opinion of the Investigator

All AEs that occur after any subject has been screened, enrolled, before treatment, during treatment, or within 30 days following the cessation of treatment, whether or not they are related to the study, must be recorded on forms provided by the Sponsor or its representative.

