12.4. Recording Adverse Events

Adverse events spontaneously reported by the subject and/or in response to an open question from the study personnel or revealed by observation will be recorded during the study at the investigational site. Clinically significant changes in laboratory values, blood pressure, and pulse rate need not be reported as AEs per the Investigator's judgement. However, abnormal values that constitute an SAE or lead to discontinuation of administration of study drug must be reported and recorded as an AE. Information about AEs and SAEs will be collected from the signing of the informed consent form until 30 days following the last dose of study drug. The S/AE term should be reported in standard medical terminology when possible. For each S/AE, the Investigator will evaluate and report the onset (date and time), resolution (date and time), intensity, causality, action taken, serious outcome (if applicable), and whether or not it caused the subject to discontinue the study/study treatment.

Intensity will be assessed according to the following scale:

- Mild (awareness of sign or symptom, but easily tolerated)
- Moderate (discomfort sufficient to cause interference with normal activities)
- Severe (incapacitating, with inability to perform normal activities)

It is important to distinguish between serious and severe AEs. Severity is a measure of intensity, whereas seriousness is defined by the criteria under Section 12.2.1.2. An AE of severe intensity may not be considered serious.

Should a pregnancy of a subject or partner occur, it must be reported and recorded on the Sponsor or its representatives' pregnancy form. Pregnancy in itself is not regarded as an AE unless there is a suspicion that the investigational product may have interfered with the effectiveness of a contraceptive medication. Reports of pregnancy must be submitted to Syneos Health Safety & Pharmacovigilance within one business day:

Email Address: [contact]

Fax no. Americas: [contact]

Fax no. Europe and ROW [name]

The outcome of all pregnancies (spontaneous miscarriage, elective termination, normal birth or congenital abnormality) must be followed up and documented even if the subject was discontinued from the study.

All reports of congenital abnormalities/birth defects are SAEs. Spontaneous miscarriages should also be reported and handled as SAEs. Elective abortions without complications should not be handled as AEs.

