3.3. Brief Description

This is an international, multicenter, open-label, long-term extension study evaluating the safety of ecopipam tablets for the treatment of children and adolescent subjects with TS. Subjects who completed the Phase 2b, randomized double-blind efficacy and safety study (EBS-101-CL-001) and who continue to meet the inclusion/ exclusion criteria for this study will be eligible to participate in this study. All subjects will be titrated to a target dose of 2 mg/kg/day as subjects participating from previous studies will be tapered down from study medication to maintain the blind. Subjects will complete study visits every month for 1 year. Follow Up visits will be conducted 7 and 14 days after the last dose of study medication and a Follow Up phone call will be conducted 30 days after the last dose of study medication. Study Visits may be completed in locations other than clinic and/or safety and efficacy assessments required at these visits will be made available for remote administration due to restrictions as a consequence of the COVID-19 pandemic or other qualifying event.

Safety will be monitored throughout the study at all visits by repeated monitoring of adverse events (AEs), vital signs, the Columbia-Suicide Severity Rating Scale (C-SSRS), the Abnormal Involuntary Movement Scale (AIMS), the Barnes Akathisia Rating Scale (BARS), the Pediatric Anxiety Rating Scale (PARS) and Children's Depression Rating Scale-Revised (CDRS-R). In addition to these assessments, at Baseline, Months 1, 3, 6, 9 and 12 safety will also be monitored by clinical and laboratory evaluations, and electrocardiogram (ECG) monitoring. In addition to the scales aforementioned, the Yale Global Tic Severity Scale (YGTSS), Clinician Global Impression of Tourette Syndrome of Severity (CGI-TS-S), the Clinician Global Impression Tourette Syndrome of Improvement (CGI-TS-I) and the Gilles de la Tourette Syndrome—Quality of Life Scale for Children and Adolescents (C&A-GTS-QOL) will also be assessed at Baseline, Months 1, 3, 6, 9 and 12. At the Follow Up visits, AE monitoring, the C-SSRS, clinical and laboratory evaluations and vital signs will be assessed. A Follow Up phone call will be conducted 30 days after the last dose of study medication to assess AEs. Subjects will be monitored for signs of abuse, and withdrawal or dependence.

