6.2. Key Definitions

Treatment emergent adverse events (TEAEs) are defined as any adverse events that start or increase in intensity on or after the first dose of open-label treatment on Day 1.

Duration of exposure is defined as (Date of Last Dose – Date of First Dose) +1. If date of last dose is unknown, then the date of last clinical visit will be used to impute the date of last dose.

Baseline is defined as the last measurement taken before the first dose of open-label treatment on Day 1.

Change from baseline will be calculated for the post-baseline assessment as post-baseline value – baseline value.

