9.3. Adverse Events (AEs)

An AE is any untoward medical condition that occurs in a subject while participating in this clinical study. The AEs will be coded to system organ class (SOC) and preferred term (PT) using the MedDRA dictionary, version 25.0. The National Cancer Institute Common Terminology Criteria for Adverse Events (NCI-CTCAE), version 4.03 will be used to assess the severity of AEs.

All AEs that occur after the first study drug administration and up to 30 days after the subject's last study drug administration will be considered treatment-emergent adverse events (TEAEs).

This document is confidential.

Summaries will focus on the TEAEs (simply referred to as adverse events in summary tables). A subject with 2 or more TEAEs within the same level of summarization (i.e., SOC or PT) will be counted only once in that level using the most severe event or most related event.

Summaries presenting the frequency of AEs by SOC and PT will be sorted by descending frequency of SOC and then, within a SOC, by descending frequency of PT.

The following summary tables will be provided:

- 1) An overall summary with the number and percentage of patients reporting AEs, serious AEs, grade 3 or higher AEs, treatment-related AEs, AEs leading to study treatment discontinuation and AEs with outcome of deaths.
- 2) AEs and Treatment-Related Adverse Events (TRAEs) by maximum severity
- 3) AEs and Serious Adverse Events (SAEs) by maximum relatedness
- 4) AEs overall and by SOC and PT
- 5) AEs overall and by SOC, PT and highest CTCAE grade
- 6) TRAEs overall and by SOC and PT
- 7) TRAEs overall and by SOC, PT and highest CTCAE grade
- 8) AEs leading to study treatment termination overall and by SOC and PT
- 9) AEs leading to study treatment termination overall and by SOC and highest CTCAE grade
- 10) CTCAE Grade 3 or higher AEs, overall and by SOC and PT
- 11) SAEs overall and by SOC and PT

A SAE is an AE which falls into one or more of the following categories:

- a. Results in death
- b. Is life-threatening
- c. Requires inpatient hospitalization or prolongation of existing hospitalization
- d. Results in persistent or significant disability or incapacity
- e. Is a congenital anomaly/birth defect
- f. Is any other important medical event

- 12) SAEs overall and by SOC and PT and by age group (children 6-12 and adolescents 13-18)
- 13) Adverse Event of Special Interests (AESIs) overall and by SOC and PT

This document is confidential.

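### The final adverse-event phone call may be made from day 27, so up to 3 days of the 30-day reporting period can pass without a scheduled enquiry

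*SAP*

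**What the plan says.** **Timing of the call.** The last column of the schedule in SAP 17.1 is the follow-up phone call, placed at "30 Days After Last Dose". The Visit Window row gives plus or minus 3 days and runs through that column, both there and in the current Protocol Table 2. The running text gives the call a purpose but no tolerance: "A Follow Up phone call will be conducted 30 days after the last dose of study medication to assess AEs" (SAP 3.3; the protocol synopsis and Protocol 7.1 say the same). In Protocol Table 2, adverse events are the only assessment marked for the call. The contact before it is the second follow-up visit, nominally 14 days after the last dose.

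**Period for recording.** Protocol 12.4 states: "Information about AEs and SAEs will be collected from the signing of the informed consent form until 30 days following the last dose". Protocol 12.2.1 says that events "within 30 days following the cessation of treatment, whether or not they are related to the study, must be recorded on forms". Sections 12.2.1.2 and 12.5 set the same limit for SAEs.

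**Period for counting.** SAP 9.3 has events "up to 30 days after the subject's last study drug administration will be considered treatment-emergent adverse events (TEAEs"), and Protocol 13.2.1 agrees. SAP 6.2 defines TEAEs differently, as "any adverse events that start or increase in intensity on or after the first dose of open-label treatment on Day 1", with no upper limit.

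**The concern.** The call closes a fixed period, so it can cover the whole period only if it is made at or after the period's end. A symmetric tolerance suits a clinic visit that measures a current state. It does not suit a contact that looks back over an interval, because a call made early looks back over less of it.

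Protocol 12.4 names three routes by which an AE comes to light: spontaneous report, an open question from study staff, and observation. After a call on day 27, neither a question nor an observation is scheduled for days 28 to 30. Only spontaneous report remains.

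Long-term safety is the primary objective. Protocol 12.1 asks for monitoring of withdrawal and dependence, and SAP 9.3 lists withdrawal, depression and self-injury among the events of special interest. In Protocol Table 2 the C-SSRS is last given at Visits 14 and 15, which leaves the call as the final enquiry of any kind. The planned outputs would not show the shortfall either: the disposition summary in SAP 7.1 has no count tied to AE follow-up through day 30. SAP 6.4 does not help, since its visit windowing excludes follow-up visits and does not concern AE collection.

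**Working it through.** The plan gives no figure for completeness of AE follow-up, so there is none to reproduce. The check is day arithmetic, with the day of last dose as day 0.

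**Inputs**
- Nominal call day: 30 (SAP 17.1, Protocol Table 2).
- Tolerance: 3 days either way (same tables, Visit Window row).
- End of the AE, SAE and TEAE period: day 30 (Protocol 12.2.1, 12.2.1.2, 12.4, 12.5, 13.2.1; SAP 9.3).
- Previous contact: nominally day 14, also with a tolerance of 3 days, so days 11 to 17.

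**Permitted call days.** Earliest 30 − 3 = 27; latest 30 + 3 = 33.

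**Days left without a scheduled enquiry** = max(0, 30 − call day):

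| Call on day | 27 | 28 | 29 | 30 | 31 | 32 | 33 |
|---|---|---|---|---|---|---|---|
| Days not covered | 3 | 2 | 1 | 0 | 0 | 0 | 0 |

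**Largest loss for one subject.** 3/30 = 10% of the post-dose period. As a share of the days that only this call covers: 3/(30 − 14) = 3/16 = 19% with the previous visit on day 14. The range is 3/(30 − 11) = 3/19 = 16% to 3/(30 − 17) = 3/13 = 23% over that visit's own window.

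**Share of subjects affected.** This depends on when sites call, which the documents do not say. If every call is on day 30 or later, it is 0%. If every call is on days 27 to 29, it is 100%. The mean loss accordingly lies between 0 and 3 days per subject. An even spread over the seven permitted days would give 3/7 = 43% of subjects and (3 + 2 + 1)/7 = 0.86 day on average. That spread is an assumption made only to place a point inside the range; nothing in the documents supports it.

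**With a window of 0/+3 days.** Permitted days are 30 to 33, and the days not covered are 0, 0, 0, 0.

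**The case against.** A reader might infer that a compliant site can close AE collection on day 27. The documents do not support that. No section says collection ends with the call, and Protocol 12.4 sets the period independently of it: information "will be collected from the signing of the informed consent form until 30 days following the last dose of study drug". A site that ignored an event on day 29 because its call was already made would breach the protocol. Protocol 12.5 goes further and asks for possibly or probably related SAEs to be reported whenever the investigator discovers them. The events most likely to be lost are therefore non-serious or unrelated ones that nobody volunteers. This part of the objection stands in full. What it leaves is a narrower gap: a duty to record an event is not a means of learning about it.

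Two other inferences go too far. One is that a subject called early counts as fully followed: neither document defines complete AE follow-up or ties study completion to day 30. The other is that the window can only lower event counts. Early calls can only lose events, but the SAP's two TEAE definitions differ. Under the open-ended one in 6.2, a call on days 31 to 33 could add events with onset after day 30; under 9.3 it could not. The net direction depends on which definition is applied, and that inconsistency is a separate matter to reconcile.

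It is also fair to say that the running text names day 30 without a tolerance, so many sites may call on or after it. That bears on how often the gap occurs, not on whether the schedule permits it.

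Finally, SAP section 10 lists updates made after database lock. The call dates in this study are fixed, and changing the schedule cannot recover anything. That stands, and it limits what the fix can do here.

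**Conclusion.** The point holds as a mismatch between a contact window and the period that contact is meant to close. A site can make its last scheduled AE enquiry on day 27 with no visit-window deviation, leaving onsets on up to 3 of 30 post-dose days (10%) to spontaneous report. The obligation to record and report through day 30 is intact.

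The proportion of subjects affected cannot be stated from the documents (0% to 100%), and the expected number of missed events is small. The conclusion assumes that the Visit Window row applies to the phone call as printed and that no further contact after an early call is arranged outside these documents. I would class it as a cheap improvement, not a threat to the study's conclusions.

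**What to change.** 1. In Protocol Table 2 and SAP 17.1 together, make the window for this one contact agree with the 30-day AE period so that it does not open before day 30, for example 0/+3 days. Changing only the SAP would set it against the protocol, which governs conduct.
2. In the SAP, add a count of subjects whose last AE contact was on or after day 30, alongside the disposition summary (7.1) or the AE tables (9.3).

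**Cost.** The first is one cell in each schedule, but it needs a protocol amendment with IRB or IEC approval (Protocol 16.1). Some calls would come up to 3 days later. It cannot change data already collected, so for this study its value is limited to any later use of the schedule. The second is one table row and can still be produced after lock, assuming the call date was recorded. It would also replace the 0% to 100% range above with the actual figure.
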